8.1. Sample size determination

A sample size of 140 participants (70 in each arm) was calculated to detect the difference between arms at two-sided type I error of 0.05 and power of 80% according to results of the pilot study [17]. Number of patients with any AESI was 33% in a control group and 11% in interventional group. A 10% dropout rate was already included in a total number.

8.2. Analysis of primary endpoint

The primary endpoint will be evaluated as number and percentage of patients with any AESI defined in section 2.2 and compared between study arms by Chi-square test or Fisher exact test. The difference between proportions including its 95% CI will be calculated as well. FAS and PPS will be used for the analysis of the primary endpoint.

8.3. Analysis of secondary objective(s) and endpoint(s)

All secondary endpoints will be analysed using FAS. Descriptive statistics and statistical tests described above will be used based on the type of variables and fulfilment of criteria for the usage of particular tests.

The incidence of any adverse events and reactions will be analysed descriptively and compared between study arms in the same manner as the primary endpoint

Duration of surgery will be analysed descriptively and compared between study arms.

ICU and hospital length of stay (LOS) will be calculated as a number of days between admission and discharge, analysed descriptively and compared between study groups.

28-days mortality will be evaluated as a number and percentage of patients who are not alive 28 days after randomization and compared between study arms.

Hemodynamic characteristics, blood parameters (hemoglobin, plasma lactate level) and their changes over time will be analysed descriptively and compared between study arms.

Fluid balance and fluid therapy will be analysed descriptively and compared between study arms.

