7.2. AE surveillance, recording and documentation

AE could be diseases or symptoms which occur or worsen after the enrolment of a patient in the clinical trial. All AEs need to be documented, no matter if the investigator suspects a causal

connection to the study medication. AE will be monitored and documented **from the day of giving informed consent until the end of participation in the study** (i.e., End of Study Visit or Premature withdrawal Visit).

Subjects will be instructed to report any AEs that they experience to the investigator. The investigator should actively ask about AEs and record the potential AE.

Each AE should be described, documented in the eCRF, and evaluated to determine:

- Seriousness (see Chapter 7.4);
- Severity (see Chapter 7.5);
- Causality, i.e. relation to the study medication (see Chapter 7.6);
- Duration (start and end dates or whether it continues).
- Action taken (no action taken; study medication discontinued; prolongation of the ongoing hospitalization; administration of a drug etc.)

AE needs to be **followed until its resolution**, i.e. until it subsides, stabilizes, becomes chronic, or the subject dies.

If AE fulfils the criteria of **SAE**, **separate form in eCRF** must be completed (see Chapter 7.7).

AEs will be recorded according to the Medical Dictionary for Regulatory Activities (MedDRA). The most recent MedDRA version at the start of the study will be used.

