7.5. Assessment of intensity (severity)

The intensity (severity) of an AE should be evaluated according to these 5 categories:

Grade 1	AE is asymptomatic or mildly symptomatic, requires only observation, no medical intervention
Grade 2	AE with medium intensity, requires local, non-invasive, or small-scale treatment
Grade 3	AE is medically significant, requires hospitalization or extension of ongoing hospitalization, but it is not directly life-threatening

Grade 4	AE is life-threatening and requires urgent significant medical intervention
Grade 5	AE leads to death

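### The one named between-arm comparison of all adverse events is any event yes/no across Grades 1 to 5; adding a graded comparison would use data the trial already collects.

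*Protocol*

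**What the plan says.** Section 8.3 has the incidence of any adverse events and reactions described and then "compared between study arms in the same manner as the primary endpoint". Section 8.2 supplies the manner: the primary endpoint is "evaluated as number and percentage of patients with any AESI", tested by Chi-square or Fisher, with the difference in proportions and its 95% CI.

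The events entering the 8.3 comparison are unrestricted. Section 7.2 states: "All AEs need to be documented, no matter if the investigator suspects a causal" link to the study medication, and recording runs from consent to the end of participation. The lowest of the five grades in 7.5 reads: "AE is asymptomatic or mildly symptomatic, requires only observation, no medical intervention". Section 7.2 also has seriousness and severity evaluated for each event. Chapter 8 names no between-arm comparison that uses either.

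Two statements limit the weight of this comparison. Section 2.3 lists the endpoint as a descriptive analysis, and the introduction to Chapter 8 makes all tests exploratory, with P < 0.05 as the mark of statistical significance.

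**The concern.** The yes/no cut suits the primary endpoint, because the AESI list in 2.2 is selective and most items count only when moderate or severe. The set of all AEs has no such threshold. A patient with one asymptomatic event needing observation only and a patient with a life-threatening event contribute the same YES.

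This has two consequences. A pure shift in severity, where the same patients have events but of a worse or milder grade, leaves the any-AE percentages unchanged. A difference in one class of events is diluted by every patient who has some other event anyway.

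Safety is part of the stated aim (2.1). Apart from 28-day mortality, this is the only named between-arm comparison of adverse events that reaches beyond the AESI list. Nearly equal percentages with a non-significant p-value could be taken as evidence of equal safety when the comparison had little ability to show otherwise, in either direction.

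**Working it through.** **Inputs from the protocol (8.1).** Size: "A sample size of 140 participants (70 in each arm"). Error and power: "two-sided type I error of 0.05 and power of 80"%. Assumed rates: "Number of patients with any AESI was 33% in a control group and 11% in interventional group". The 140 already contains an allowance of 10% for dropout. Evaluable per arm: 70 × 0.9 = 63.

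**The plan's own figure.** Exact Fisher power for 33% vs 11% is 80.5% at 62 per arm and 81.4% at 63; 63 / 0.9 = 70 per arm, 140 in total. The continuity-corrected formula gives 64 per arm, 72 after dropout, 144 in total. The uncorrected formula gives 55, 62 and 124. The stated 140 therefore reproduces under the exact Fisher test.

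**Assumption, not in the protocol.** A share b of patients has at least one AE that is not an AESI, equal in both arms and independent of AESI.

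**Dilution.** Any-AE rate = 1 − (1 − p)(1 − b), with p the AESI rate. The difference between arms is (0.33 − 0.11)(1 − b) = 0.22(1 − b). Power is exact for the two-sided Pearson chi-square test at 63 per arm.

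| b | Control | GDHT | Difference (points) | Power |
|---|---|---|---|---|
| 0 | 33.0% | 11.0% | 22.0 | 86% |
| 20% | 46.4% | 28.8% | 17.6 | 55% |
| 30% | 53.1% | 37.7% | 15.4 | 44% |
| 50% | 66.5% | 55.5% | 11.0 | 26% |
| 70% | 79.9% | 73.3% | 6.6 | 14% |
| 80% | 86.6% | 82.2% | 4.4 | 10% |
| 90% | 93.3% | 91.1% | 2.2 | 7% |

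With all 70 per arm (normal approximation) the change is negligible: 26%, 11% and 7% at b = 50%, 80% and 90%.

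The cause is dilution by events common to both arms, not a high rate as such. A full 22-point difference from 90% to 68% would keep about 87% power at 63 per arm (normal approximation).

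**What a graded comparison would add.** Take the worst grade per patient in three classes (none, Grade 1–2, Grade 3+), with a tie-corrected Mann-Whitney test, simulated. Let g be the share of AESI patients reaching Grade 3+, and h the share of patients in each arm with a non-AESI Grade 3+ event. Both are assumptions. Then P(none) = (1 − p)(1 − b) and P(Grade 3+) = 1 − (1 − g·p)(1 − h). Each Mann-Whitney cell shows power for g = 0.5 / g = 1.

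| b | Any AE | Worst grade, h = 0 | Worst grade, h = 20% | Worst grade, h = 30% |
|---|---|---|---|---|
| 30% | 44% | 54% / 66% | 37% / 49% | 31% / 41% |
| 50% | 26% | 43% / 64% | 28% / 45% | 22% / 37% |
| 90% | 7% | 41% / 77% | 20% / 49% | 15% / 39% |

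At b = 90% the worst-grade comparison is better in every case shown. At b = 50% it gains 17 to 38 points with h = 0, about 2 points with h = 20% and g = 0.5, and loses about 4 points with h = 30% and g = 0.5. At b = 30% with h = 20% and g = 0.5 it loses 7 points.

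**The case against.** The strongest reply is that nothing here is an error. The percentage of patients with any AE is a conventional summary. The same sentence of 8.3 promises a descriptive analysis, tables by grade and seriousness commonly belong in the SAP, and every test is exploratory. This stands as far as it goes: the point is an improvement, not a contradiction. However, 8.3 does more than leave detail open. It fixes the form of the between-arm comparison, and a SAP that follows it inherits that form.

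Four stronger readings are tempting, and the protocol does not support them.

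- A reader might infer that the any-AE rate is certain to be near its ceiling. The protocol gives no such rate. It offers only hints, such as decreased hematocrit listed as very common with the colloid (5.2.6). At b = 20% power is still 55%.
- A reader might infer that severity is discarded altogether. It is not: the descriptive analysis remains, most AESIs carry a severity threshold, and 28-day mortality is compared separately.
- A reader might infer that the trial would miss the difference it was sized on. It would not, because any AESI is the primary endpoint and is tested undiluted. The 22 points serve here only as a yardstick. What the all-AE comparison adds is information on other events, and the protocol gives no expected difference for those.
- A reader might infer that a worst-grade test is always more powerful and should replace the yes/no comparison. The second table shows otherwise. Grade 3 in 7.5 includes events that prolong the hospital stay, so non-AESI Grade 3 events cannot be assumed absent.

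**Conclusion.** The point holds as a small, conditional improvement to a secondary, exploratory safety comparison. It is certain from the text that the named comparison treats all grades alike and cannot register a pure shift in severity. How much else is lost depends on an any-AE background that the protocol does not state: power for the diluted 22-point difference is about 26%, 10% and 7% at b = 50%, 80% and 90%, assuming equal and independent background events and 63 patients per arm.

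The benefit of grading is also conditional. At b = 90% it is 41% to 77% against 7% if no non-AESI event reaches Grade 3, and 20% to 49% against 7% if 20% of patients have one. At lower b it can be nil or negative. This supports adding a graded comparison alongside the any-AE comparison, not substituting it. The primary analysis is unaffected. Even with the addition, a non-significant result would not establish equal safety; the confidence intervals should carry the interpretation.

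**What to change.** In 8.3, keep the percentage of patients with any AE and add text along these lines:

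*The numbers and percentages of patients with any Grade 3 or higher AE and of patients with any SAE will be compared between arms, each with the risk difference and its 95% CI. The worst AE grade per patient (none, Grade 1 to 5; section 7.5) will be compared by the Mann-Whitney test, with the probability of a worse grade and its 95% CI. A non-significant difference in the percentage with any AE will not be interpreted as equal safety.*

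Carry the same text into the SAP. The cost is a short addition to each document, a few more exploratory comparisons, and one effect measure that is less familiar to readers. Grade and seriousness are already recorded in the eCRF for every AE, so no new data, procedures or patients are needed.

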2.3. Secondary objective(s) and endpoint(s)

The **secondary objective** is to investigate the efficacy and additional safety parameters of GDHT guided by non-invasive advanced hemodynamic monitoring versus hemodynamic management guided by standard vital signs monitoring.

Secondary endpoints are as follows:

1.) Additional safety information

Monitored parameters:

- Duration of surgery (min)
- LOS (day of admission – day of discharge will be counted as 1 day)
- ICU LOS (day of admission – day of discharge will be counted as 1 day)
- 28-day mortality (number of patients who are not alive 28 days after randomization)
- Descriptive analysis of the incidence of any adverse events and reactions

2.) Comparison of hemodynamic characteristics and their changes over time between study groups

Monitored parameters:

- MAP (mmHg; before, after surgery)
- HR (Bpm; before, after surgery)
- SVV (%; before, after surgery)
- Number of episodes of hypotension¹
- Number of vasopressor administrations

3.) Comparison of laboratory values of selected blood parameters and their changes over time between study groups

Monitored parameters:

- Hemoglobin (g/l; before, after surgery and 24 hours after surgery)
- Plasma lactate level (mmol/L; before, after surgery and 24 hours after surgery)

4.) Comparison of fluid balance and fluid therapy between study groups

Monitored parameters:

- Volume of blood loss (ml/kg; during surgery² and in the 24-hour postoperative period)
- Urinary output (ml/kg/hod; during surgery² and in the 24-hour postoperative period)
- Number of administered units of packed RBC (during surgery² and in the 24-hour postoperative period)

¹ MAP bellow 65 torrs [18]

² **duration of surgery** is considered as the time from the skin incision to the suture of the dura

- Number of subjects receiving transfusion (during surgery² and in the 24-hour postoperative period)
- Crystalloid and colloid solutions consumption (type and total volume of infusion during surgery² and in the 24-hour postoperative period)
- Boluses of crystalloids (ml; during surgery²)

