4.3. Randomization

Participants will be randomized in a 1:1 ratio to the two study arms (GDHT or STANDARD) using the eCRF REDCap database shortly before surgery by a member of the study team.

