6. COURSE OF THE TRIAL

6.1. Screening of eligible patients

Adult patients scheduled for elective neurosurgery will be screened for eligibility criteria after admission to the hospital. Study team members will perform the screening, and the principal investigator will regularly audit the accuracy of screening. Patients will be included if they meet all inclusion criteria and none of the exclusion criteria. After obtaining informed consent, each patient will be randomised to one of the trial arms. For details on obtaining the informed consent see Chapter 10.1.

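### Hospital length of stay is counted from admission, so the between-arm comparison includes pre-randomisation days that the intraoperative intervention cannot affect

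*Protocol*

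**What the plan says.** The protocol defines hospital stay twice, each time starting at admission. The endpoint list in Section 2.3 has "LOS (day of admission – day of discharge will be counted as 1 day", and Section 8.3 states that "ICU and hospital length of stay (LOS) will be calculated as a number of days between admission and discharge".

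Three other sections fix the order of events before surgery:

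- Section 6.1: patients "will be screened for eligibility criteria after admission to the hospital", and then "After obtaining informed consent, each patient will be randomised to one of the trial arms".
- Section 6.3: screening, consent and randomisation are listed under Day -3 to 0. Anaesthesia, surgery and the hemodynamic intervention fall on Day 1.
- Section 4.3: randomisation is done "using the eCRF REDCap database shortly before surgery by a member of the study team".

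On the analysis, Section 8.3 says "All secondary endpoints will be analysed using FAS". Section 8.6 defines that set as the randomised patients who had surgery. Section 8 chooses between Welch's t-test and the Mann-Whitney test after a normality check and calls all testing exploratory.

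**The concern.** The randomised comparison concerns fluid and vasoactive management that starts after induction of anaesthesia. Time in hospital before that point is a baseline feature of the patient and of the site's admission practice. Adding it to the outcome brings in variation unrelated to treatment and dilutes any real difference in recovery time.

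The protocol does not use one origin throughout. Its mortality endpoint is "28-day mortality (number of patients who are not alive 28 days after randomization", so a clock that starts at or near treatment is already in use elsewhere.

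What is at stake is precision on one secondary endpoint. Section 1.4 lists shorter hospital stays among the benefits seen with this approach in other surgical fields, so readers will look at the result. Section 1.1 is more cautious: it also cites a 76-study meta-analysis in which an effect on hospital stay was not demonstrated.

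**Working it through.** **Plan's own figure.** There is none to reproduce. The protocol gives no expected stay, SD or power for this endpoint, and the 140 patients in Section 8.1 rest on the complication rates.

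**Step 1: does the interval contain pre-randomisation time?** The order is admission, then screening and consent (Section 6.1), then randomisation shortly before surgery (Section 4.3), then surgery on Day 1 (Section 6.3). Hospital stay (Sections 2.3 and 8.3) starts at the first of these. It therefore includes pre-randomisation days for every patient admitted on a day before randomisation.

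**Step 2: is the comparison biased?** Write hospital stay as T = W + P, where W is the days from admission to surgery and P is the days from surgery to discharge. Randomisation gives W the same expected value in both arms, so W cancels from the expected difference in means. What is left is extra variance:

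Var(T) = Var(W) + Var(P) + 2 Cov(W, P).

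**Step 3: how much variance?** All inputs here are assumptions.

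- W takes the values 0, 1, 2, 3 with equal probability, independent of P.
- Mean of W = (0 + 1 + 2 + 3)/4 = 1.5.
- Mean of W squared = (0 + 1 + 4 + 9)/4 = 3.5.
- Var(W) = 3.5 - 1.5² = 1.25 days².

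| Assumed SD of P (days) | Var(P) | Added variance, 1.25/Var(P) | Standard error multiplied by |
|---|---|---|---|
| 5 | 25 | 5% | √1.05 = 1.02 |
| 3 | 9 | 14% | √1.139 = 1.07 |
| 2 | 4 | 31% | √1.3125 = 1.15 |

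A shorter wait costs less. If W is 0 or 1 with equal probability, Var(W) = 0.25, and the three rows become 1%, 3% and 6%. If W is the same for everyone, Var(W) = 0 and nothing is lost. If W and P are correlated, the covariance term raises or lowers these figures.

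**Step 4: what could that mean for power?** A simulation, again on assumed inputs, used 63 evaluable patients per arm (70 less the 10% dropout in Section 8.1). Post-operative stay was log-normal with median 8 days and log-SD 0.5, the true stay was 20% shorter with the intervention, and the test was Mann-Whitney, with 4,000 runs. Power was about 0.69 without pre-operative days and about 0.62 with a uniform 0 to 3 day wait. With no true effect, the rejection rate stayed near 0.05 and the mean difference near 0, which agrees with Step 2.

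**The case against.** Counting stay from admission is a conventional definition and contradicts nothing in the protocol. The wait is balanced by randomisation, its length is nowhere stated, and for many patients it may be 0 or 1 day. The Day -3 to 0 window dates screening, consent and randomisation, not admission, so it does not establish a three-day wait. The 31% needs the smallest of the three assumed SDs. The endpoint is exploratory and did not drive the sample size. All of this stands, and it limits the point to a precision improvement of unknown size.

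One part does not stand, namely that the statistical analysis plan could settle the matter. Section 8.5 leaves the handling of missing dates to that plan, whereas the start of the clock is already fixed in Sections 2.3 and 8.3.

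A reader might go further in two ways that the documents do not support.

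- **Early in-hospital deaths count as short stays.** No section equates death with discharge, and none says how such a patient enters the variable. That coding is commonly left to the statistical analysis plan, which is not at hand. Mortality at 28 days is compared separately. Giving deaths the worst rank is therefore not called for here. It would turn the endpoint into a composite with mortality and would have no meaning if Welch's t-test were the test chosen.
- **ICU stay has the same fault.** Sections 2.3 and 8.3 treat the two stays together, but the protocol does not place ICU admission before surgery. Section 6.3 mentions the intensivist only for postoperative care.

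**Conclusion.** The point holds for hospital length of stay alone. As defined, it includes days before randomisation that the intervention cannot influence. This costs precision and creates no expected bias. Under an assumed uniform 0 to 3 day wait, independent of post-operative stay, the added variance is about 5% to 31% as the post-operative SD goes from 5 down to 2 days. With a constant wait it is zero. The documents contain no figure that would narrow this range. It is a minor, optional improvement to an exploratory secondary endpoint and leaves the trial's main conclusions untouched.

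**What to change.** In Sections 2.3 and 8.3, define hospital length of stay for the between-arm comparison as the number of days from the day of surgery (Day 1) to hospital discharge. Keep admission-to-discharge stay as a descriptive summary by arm. Leave the ICU definition as it is.

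Every patient in the full analysis set has had surgery (Section 8.6), so the new origin exists for all of them. Surgery and discharge are already part of the schedule in Table 1. The cost is a wording change, with no effect on the 140 patients or the visit plan. The one drawback is that the compared figure will not match administrative length of stay, which the descriptive summary covers.

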8.4. Demographic characteristics

Demographic characteristics of patients will be analysed descriptively overall and by study arms.

8.5. Missing data

In general missing data are not planned to be imputed. For secondary endpoints defined as duration (duration of surgery, ICU and hospital length of stay (LOS)) missing dates and/or times will be imputed based on the rules further specified in the SAP, unless missing due to premature discontinuation.

For the rest of continuous variables defined as secondary endpoints proportion of missing data will be evaluated, unless missing due to premature discontinuation. If more than 50% of the expected data are missing, imputation techniques might be applied within the scope of sensitivity analysis. Further details will be provided in the SAP.

8.6. Analysis sets

Full analysis set (FAS)

FAS comprises all randomized patients who underwent surgery. All endpoints will be evaluated using FAS.

Per-protocol set (PPS)

PPS includes all patients from FAS without protocol deviations which might affect the evaluation of primary endpoint. The principal investigator will assess protocol non-adherence on a case-by-case basis. Patients with significant deviations from the study protocol will be excluded from PPS.

PPS will be used for analysis of primary endpoint.

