6.3. Study procedures

Day -3 to 0

- Eligibility screen – inclusion and exclusion criteria
- Informed consent procedure (Chapter 10.1)
- Pregnancy testing (see Chapter 7.8)
- Demographic data
- Randomization (more in Chapter 4.3)

Day 1

- Assessment of hemoglobin and plasma lactate level
- Recording blood loss and urinary output during and after surgery
- Transfusion products consumption
- Crystalloid and colloid solution consumption
- Monitoring of hemodynamic parameters
- Monitoring of adverse events and reactions including postoperative complications of special interest

Prior to surgery, study participants will receive regular premedication according to hospital standards.

General anaesthesia will be induced by intravenous administration of propofol. For attenuation of the hemodynamic response to laryngoscopy, opioid will be added. To facilitate intubation, a neuromuscular blocking agent (N MBA) will be used. After tracheal intubation, mechanical ventilation will be commenced with the following settings: tidal volume of 8–10 ml/kg and respiratory rate to maintain an end-tidal CO₂ of 30–35 mmHg. Anaesthesia will be maintained with propofol infusion using TCI (target controlled infusion) or TIVA (total intravenous anaesthesia) and additional doses of opioids and relaxants will be administered at the discretion of the attending anaesthesiologist. The patients' temperature will be maintained at 36–37 °C.

Both groups will receive standard monitoring of vital signs through continuous electrocardiography, pulse oximetry, end-tidal CO₂ measurement, and invasive monitoring of arterial blood pressure.

In the STANDARD arm, perioperative hemodynamic management and postoperative care will be at the discretion of the attending anaesthesiologist and intensivist, respectively. Hypotension with MAP < 65 mmHg will be managed with administration of a 250-ml bolus of balanced crystalloid over 10 min or 250-ml bolus of colloid over 5 min. The choice of fluid and number of boluses will be at the discretion of attending anaesthesiologist. If fluids are considered ineffective, a vasopressor will be added.

In the GDHT arm, non-invasive hemodynamic monitoring will be used (Starling™ SV hemodynamic monitor, Cheetah Medical Inc., [name], USA) in addition to the monitoring used in the STANDARD arm. The Starling SV monitor uses

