patented Bioreactance® technology and requires placement of only four sensors, which are skin electrodes similar to those used for ECG monitoring.

The extended monitoring will begin after the induction of general anaesthesia and resolution of any hypotension caused by the induction of general anaesthesia. This hypotension will be resolved with fluid bolus and vasopressor administration if necessary. Subsequently, a basal infusion will be initiated with balanced crystalloid solution at $3 \text{ ml.kg}^{-1}.\text{h}^{-1}$ with an infusion pump. We will then determine the optimal Cl^a , defined by a value of at least $2,5 \text{ l.min.m}^{-2}$, a stroke volume variation (SVV) below 15%, and a MAP above 65 mmHg. If the Cl^a will not be optimal, appropriate interventions will be performed to achieve optimal values.

In case of $\text{SVV} > 15\%$, a 250-ml bolus of crystalloid over 10 min will be administered. This process will be repeated until the SVV decrease below 15%. If the SVV is above 15%, and the Cl^a decrease with administration of a bolus of crystalloid, inotropic therapy will be introduced (dobutamine) at a dose of 2,5 mcg/kg/min and increased if necessary to achieve $\text{Cl}^a > 2,5 \text{ l.min.m}^{-2}$

If hypotension occurs with MAP below 65 mmHg and SVV below 15%, norepinephrine therapy will be initiated.

After determining the optimal Cl^a , we will aim to maintain the SVV below 15% to preserve the optimal Cl^a . When the SVV exceed 15%, and the Cl^a is lower than optimal, a crystalloid bolus (250 ml) will be administered. If, after administration of crystalloid, the SVV decrease below 15%, the Cl^a will be verified. If the Cl^a is optimal, no further action will be taken. If the Cl^a remain suboptimal, the crystalloid bolus will be repeated.

If the SVV remain above 15% despite crystalloid bolus administration, the Cl^a will be verified. If the Cl^a increase, no further action will be taken. If the Cl^a is suboptimal, inotropic therapy will be introduced (dobutamine).

In case of hypotension with MAP below 65 mmHg concurrent with an SVV above 15%, a 250-ml balanced crystalloid bolus will be administered. If hypotension with MAP below 65 mmHg and SVV below 15% occurs, norepinephrine therapy will be started.

Day 2

- Assessment of hemoglobin and plasma lactate level
- Recording blood loss and urinary output during and after surgery
- Transfusion products consumption
- Crystalloid and colloid solution consumption

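### The FAS used for every endpoint requires that surgery took place, so a patient harmed after induction whose operation is abandoned can drop out of every planned between-arm analysis

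*Protocol*

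**What the plan says.** - **Analysis sets (Protocol 8.6).** "FAS comprises all randomized patients who underwent surgery. All endpoints will be evaluated using FAS". The second set is nested in the first: "PPS includes all patients from FAS without protocol deviations which might affect the evaluation of primary endpoint". No all-randomised or all-treated set is defined.
- **Use of the sets.** Section 8.2: "FAS and PPS will be used for the analysis of the primary endpoint". Section 8.3: "All secondary endpoints will be analysed using FAS". The secondary endpoints in section 2.3 include 28-day mortality and the incidence of any adverse event or reaction.
- **Randomisation (4.3).** It is done "using the eCRF REDCap database shortly before surgery by a member of the study team".
- **Start of the GDHT intervention (6.3).** "The extended monitoring will begin after the induction of general anaesthesia and resolution of any hypotension caused by the induction of general anaesthesia". The basal infusion follows, then boluses, dobutamine or norepinephrine according to the measured values.
- **Start of surgery.** The only definition is footnote 2 of section 2.3, where the duration of surgery "is considered as the time from the skin incision to the suture of the dura". Section 8.6 does not say what counts as having undergone surgery for FAS membership.
- **Event recording.** Section 7.2 has AEs documented from consent to the end of participation. Table 1 also collects AEs and AESIs at premature termination. Section 7.7 requires every SAE to reach the sponsor within 24 hours.

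**The concern.** FAS membership depends on something that happens after randomisation and, in the GDHT arm, can happen after study treatment has begun. Arrhythmia, cardiac arrest and cardiogenic pulmonary oedema are all components of the primary endpoint (2.2). The product sections list fluid overload with heart failure in susceptible patients (5.1.6) and anaphylactic reactions up to shock (5.2.6). If such an event led the team to abandon the operation before it began, the patient would leave both numerator and denominator of the primary analysis, the any-AE comparison and the mortality comparison.

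An exclusion that the allocated treatment can bring about breaks the protection that randomisation gives. Here it would remove early, severe harms from a trial whose stated aim includes the safety of GDHT (2.1). A later SAP could add a safety set, but it would have to depart from the protocol's rule that the FAS serves all endpoints.

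**Working it through.** **1. Order of events for one patient (GDHT arm)**

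| Step | Source | In the FAS if the operation is abandoned at this point? |
|---|---|---|
| Randomised | 4.3 | No |
| Anaesthesia induced, induction hypotension resolved | 6.3 | No, unless surgery is read to include anaesthesia |
| Study monitoring, basal infusion, boluses, vasoactive drugs start | 6.3 | No, on the same reading |
| Skin incision | 2.3, footnote 2 | Probably yes |

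The gap is the third row. That this row precedes incision is an inference: section 6.3 ties the start to induction and does not mention incision. It is a natural reading, because the sequence runs on directly from induction.

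**2. Could another set recover the patient?** The PPS lies inside the FAS, and 8.2 and 8.3 name no other set. So no planned between-arm analysis would include the patient.

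**3. Sample size, as a check on the planning rates.** Inputs from 8.1: 33% versus 11%, two-sided 0.05, 80% power, 10% dropout included, 140 in total. Exact power of Fisher's test at 63 per arm is 81.4%, and 63/0.9 = 70 per arm, or 140. The continuity-corrected formula gives 64 per arm; 64/0.9 = 71.1, rounded up to 72, or 144 in total. The planned figure reproduces, and this point does not affect it.

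**4. Size of the effect at the planned rates.** Expected events are 0.33 × 70 ≈ 23 in STANDARD and 0.11 × 70 ≈ 8 in GDHT. Let k be the number of GDHT patients with an AESI after study treatment starts who are never operated on, in addition to the 8 events among operated patients. The documents give no value for k; 0 to 2 is an assumption. The FAS rate is 8/(70 − k). With those patients kept, it is (8 + k)/70. STANDARD is 23/70 = 32.9% throughout. P-values are from the uncorrected chi-square test.

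| k | GDHT rate, FAS | Risk difference | p | GDHT rate, all kept | Risk difference | p |
|---|---|---|---|---|---|---|
| 0 | 8/70 = 11.4% | 21.4 points | 0.002 | 8/70 = 11.4% | 21.4 points | 0.002 |
| 1 | 8/69 = 11.6% | 21.3 | 0.003 | 9/70 = 12.9% | 20.0 | 0.005 |
| 2 | 8/68 = 11.8% | 21.1 | 0.003 | 10/70 = 14.3% | 18.6 | 0.010 |
| 5 | 8/65 = 12.3% | 20.5 | 0.005 | 13/70 = 18.6% | 14.3 | 0.053 |

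In this scenario, where the lost events are all in the GDHT arm, the exclusion favours GDHT. One or two patients shift the risk difference by 1.3 to 2.5 points and leave the conclusion unchanged. It takes five, beyond the assumed range, to carry p past 0.05.

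**The case against.** The strongest defence is that the primary objective concerns postoperative complications (2.2), and a patient never operated on has no postoperative course. A cancellation before induction cannot be caused by an intervention that starts after induction. This stands: leaving out patients who were never induced is defensible, and the dispute is confined to the interval between induction and incision.

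It can also be said that 8.6 leaves undergoing surgery undefined, that footnote 2 was written for durations and volumes rather than FAS membership, and that a broad reading could keep an anaesthetised patient in. That stands too, and it is why the conclusion is that such a patient could be lost, not that the patient certainly would be. An undefined membership rule still needs settling.

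Four stronger readings are tempting, and the documents do not support them:

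- **That such harm is counted nowhere.** Sections 7.2 and 7.7 and Table 1 show that it is recorded and, if serious, reported. It is missing only from the planned comparisons.
- **That any harm stopping the operation is lost.** Once the incision is made, the patient most likely stays in the FAS.
- **That one lost patient could decide significance.** Counts can be found that do this: 10/70 versus 19/70 gives p = 0.061, and dropping one GDHT patient with an event gives 9/69 versus 19/70, p = 0.038. Those are not the planned rates, and the crossing occurs only with the uncorrected chi-square. Fisher's test moves from 0.094 to 0.056 and the continuity-corrected test from 0.095 to 0.063. Section 8 also calls all testing exploratory.
- **That the randomisation timing is contradictory.** Section 6.3 lists randomisation in a Day -3 to 0 window shared with screening and consent and refers back to 4.3, whose timing fits inside that window.

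Nor do the documents say who decides to abandon an operation. Section 4.4 blinds the neurosurgeon, so a claim that the decision is made with knowledge of the arm would go too far.

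**Conclusion.** The point holds in a limited form. The protocol fixes an analysis set that depends on a post-randomisation event, applies it to every endpoint, and provides no set of treated patients. A patient harmed between the start of the GDHT intervention and incision, whose operation is then abandoned, could be absent from every planned between-arm analysis although the event is on record.

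The numerical effect is probably small. With 0 to 2 patients affected (an assumption), the primary risk difference changes by at most about 2.5 points at the planned rates, and the p-value stays at or below about 0.01. The case for change rests on avoiding an exclusion that treatment can cause and on complete safety reporting. It depends on two readings: that the intervention begins before incision, and that undergoing surgery means at least that the operation started. It deserves correction because the repair is simple, not because the primary result is in danger.

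**What to change.** In section 8.6, define the FAS as all randomised patients in whom anaesthesia was induced, analysed in the arm to which they were randomised whether or not surgery was completed. Use it for the primary endpoint, AEs and mortality. If the sponsor prefers to keep an operated-patient FAS for the efficacy-type endpoints, the minimum is to add a safety set with the induction-based definition for AESIs, AEs and 28-day mortality, to amend the sentence assigning all endpoints to the FAS, and to state what undergoing surgery means. In either case, list randomised patients who were not induced or not operated on, by arm with reasons.

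The cost is one definition and one listing, with no extra data collection, because these patients' events are already recorded. The small downside is that an abandoned case stays in the denominator without operative data, so summaries of surgery duration and intraoperative volumes will have fewer observations than the FAS. No change to the timing of randomisation is needed for this point.
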